### **Study budget**

The study was supported by The Scientific and Technological Research Council of Turkey 1002-Short Term Funding Program (number:215S656).

### **Hypotheses of the study**

1. Extremity function restrictions will be lower in the intervention group than in the control group.
2. Self-efficacy levels will be higher in the intervention group than in the control group.
3. Functions improving the quality of life will be higher in the intervention group than in the control group.
4. There will be fewer symptoms reducing the quality of life in the intervention group than in the control group.
5. The incidence of lymphedema will be lower in the intervention group than in the control group.

6. The mean cost of the intervention group at home visits, will be lower than in the control group.

### **Statistical analysis plan**

Data obtained in this study were analyzed with SPSS 21.0. Multifactorial variance analysis of repeated measures was used to compare the groups in terms of dependent variables, the significance test of difference between two means to compare pretest and posttest measures, one-way variance analysis of repeated measures to compare intragroup pretest and posttest measures and t-test for dependent groups with Bonferroni correction to perform further analysis of the difference between the mean scores of the groups. Intention-to-treat (ITT) analysis was utilized to eliminate effects of dropouts from the study, to maintain randomization. To prevent bias the database were analyzed by a statistician who was independent of the study.

Costs of treatments likely to be given for lymphedema in the intervention group and the control group due to the potential incidence of this condition and HBM based nursing interventions to be offered at home visits were made. The costs of the nursing interventions included time spent by the researcher at home visits, transportation for these visits, reminders on the phone, education material and tape measure. The cost of treatment for lymphedema included costs of medical treatment of an individual with stage I/II lymphedema in upper extremities in hospital. It was based on opinions of three experts. To calculate the costs from the perspective of Social Security Institution, prices of services and materials reported in Health Services Bulletin issued in Mar 2017 were taken. The expenses directly made by the patients were determined by the mean value of prices obtained from three national firms.

[figure not shown]

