### **Protocol**

Oral informed consent was obtained from the eligible women at the initial interviews on the phone. The women who agreed to participate in the study were assigned to the groups according to the research randomizer software. The women assigned to experimental and control groups were planned first home visit and obtained written informed consent was obtained at this visits. At the Intervention group; the researcher made pretest (baseline measurements) before the nursing interventions at the first home visit. The researcher offered education and guide about prevention of lymphedema after the baseline measurements at the first home visit. Second and third home visits were made three and six months after the first visit. At the second and the third home visits, the measurements were repeated, and the nursing interventions were maintained in the direction of the patients' individual needs.

At the control group; the researcher administered the pretests at first home visit. The measurements were repeated in the third and sixth months after the first home visit. The

researcher also given at the end of the sixth month, all of the nursing interventions, given to the intervention group, for the control group.

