### **Sample size calculation**

Before initiation of the study, to achieve 80% power, 95% confidence interval and 0.05 error range, a power analysis was made with G-power software and the sample size was found to be 14 were in each groups. However, a higher number of participants was planned to be included into the study:37 formed the intervention group, 35 formed the control group. At the end of the study, a post-hoc power analysis was made by using primary outcome variables. The post-hoc power analysis score was .98 for Q-DASH, .94 for SUPPH, .67 for the function scale (FS) and .80 for the symptom scale (SS) in EORTC QLQ-BR23.

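### The arms are compared on Q-DASH, SUPPH and the QLQ-BR23 scales without the baseline score as a covariate, which gives up precision the collected data could provide

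*Combined protocol and SAP*

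**What the plan says.** All references are to the combined protocol and SAP.

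- **Timing.** Under Protocol, both arms are measured at the first home visit, before any intervention. For the control arm, "The measurements were repeated in the third and sixth months after the first home visit"; the intervention arm follows the same schedule.
- **Group comparison.** Under Statistical analysis plan, "Multifactorial variance analysis of repeated measures was used to compare the groups in terms of dependent variables". No covariate is named, and no term of the ANOVA is identified as the treatment test.
- **Other tests in the same sentence.** There is a two-means significance test tied to pretest and posttest measures, with no visit or role given. There is a "one-way variance analysis of repeated measures to compare intragroup pretest and posttest measures" and a "t-test for dependent groups with Bonferroni correction to perform further analysis of the difference between the mean scores of the groups".
- **Dropouts.** "Intention-to-treat (ITT) analysis was utilized to eliminate effects of dropouts from the study, to maintain randomization". How a missing score enters the analysis is not described.
- **Hypotheses.** Hypotheses 1-4 give a direction for each scale but no time point.
- **Numbers.** Under Sample size calculation, "37 formed the intervention group, 35 formed the control group". The section adds that "At the end of the study, a post-hoc power analysis was made by using primary outcome variables", with results of .98 (Q-DASH), .94 (SUPPH), .67 (function scale, FS) and .80 (symptom scale, SS).
- **Use of baseline.** Under Randomization, a homogeneity test found no significant difference between the groups.

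**The concern.** The same woman's score before and after the intervention is usually correlated, so her baseline explains part of the spread at months 3 and 6. A covariate removes that part from the error. In a repeated-measures ANOVA, baseline is most naturally one more level of the outcome, and this uses it less well.

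The cost depends on which term is read as the answer:

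- The **group main effect** averages over baseline, where no treatment effect can exist yet. It therefore understates the effect.
- **Group-by-time** is not diluted. It uses baseline by subtraction, which is less efficient than adjustment.
- The **one-way ANOVAs within arms**, and the **t-tests for dependent groups** if read as paired, compare visits within women. They do not estimate the difference between the randomised arms.
- The **two-means test** could be an unadjusted comparison of the arms at a visit. If so, it does estimate the randomised difference, again without using baseline.

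At stake are the width of the interval for the treatment effect on all four scales, and power on the two weaker ones, FS and SS.

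**Working it through.** **Inputs.** Group sizes 37 and 35 and the post-hoc powers come from Sample size calculation. The documents give no correlation between visits, so r = 0.3/0.5/0.7 is assumed. Also assumed are SD 1, equal correlation between all visits (compound symmetry), complete data and two-sided alpha 0.05. Let h = 37×35/72 = 17.99.

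**The plan's own figures.** The 14 per group cannot be reproduced, because no effect size, SD, correlation or test is given. If the post-hoc powers are read as two-sided two-sample t-tests (df 70), they imply effects of 0.96 (Q-DASH), 0.84 (SUPPH), 0.67 (SS) and 0.57 (FS) SD.

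**Dilution of the main effect.** For visit effects (0, d, d), the three-visit mean is 2d/3. In a simulation at r = 0.5 with a true effect of 0.5, the main effect averaged 0.333 and the adjusted estimate 0.499.

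**Precision (needs no effect size).** The half-width of the 95% CI is t×√(V/h). For the mean of months 3 and 6, V is:

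- change contrast (follow-up mean minus baseline): (1+r)/2 + 1 − 2r = 1.5(1−r)
- unadjusted follow-up mean: (1+r)/2
- baseline-adjusted follow-up mean: (1+r)/2 − r²

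| | r = 0.3 | r = 0.5 | r = 0.7 |
|---|---|---|---|
| V, change contrast | 1.05 | 0.75 | 0.45 |
| V, unadjusted mean | 0.65 | 0.75 | 0.85 |
| V, adjusted mean | 0.56 | 0.50 | 0.36 |
| Half-width, change (SD) | 0.482 | 0.407 | 0.315 |
| Half-width, unadjusted (SD) | 0.379 | 0.407 | 0.434 |
| Half-width, adjusted (SD) | 0.352 | 0.333 | 0.282 |
| Narrower than change | 27% | 18% | 10.5% |
| Narrower than unadjusted | 7% | 18% | 35% |

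The variance ratio of adjusted to change is (1+2r)/3, which is below 1 for every r from 0 up to 1. If correlation decays with time (AR(1)), the ratio is 0.49/0.61/0.75, so the direction is the same.

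At a single visit, V falls from 1 to 1 − r². The half-width is then √(1−r²) = 0.954/0.866/0.714 of the unadjusted one, about 5/13/29% narrower.

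**Power, like for like (both tests two-df), FS at 0.57 SD, constant effect.**

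- Group-by-time: λ = h×(2/3)d²/(1−r) = 3.90/(1−r) = 5.57/7.79/12.99, F(2,140). Power is 54/70/90%.
- Adjusted joint test of both visits: λ = 2hd²/(1+r−2r²) = 11.69/(1.12, 1.00, 0.72) = 10.44/11.69/16.23, F(2,68). Power is 81/86/95%.
- For reference, the three-visit group main effect has 59/49/43%.

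**Adding a single averaged contrast.** The adjusted mean of the two visits has 89/92/98% for a constant effect. With the effect at one visit only, it has 36/39/51%, against 54/70/90% for group-by-time and 62/74/91% for the adjusted joint test. With the effect halved at one visit, the adjusted mean has 67/72/85% and the adjusted joint test 63/70/86%.

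**The case against.** **Group-by-time was probably the intended test.** With an assumed f = 0.25 and r = 0.5, a group-by-time test with three occasions needs exactly 14 per group (power 0.812), while the main effect needs 43. This is suggestive only, since the plan states neither input. A reader might infer that the main effect was used and that the reported effects were therefore diluted; the text does not show this. The dilution applies only on that reading. The gain over the change contrast remains if group-by-time was the test.

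**The gain depends on the comparator.** This stands. At r = 0.3 the change contrast is less precise than ignoring baseline altogether, and adjustment then gains only about 7% over the plain follow-up mean.

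**A large power gain could be credited to the covariate alone.** For FS at r = 0.3, going from 54% to 89% looks striking, but it mixes two changes: adding baseline, and replacing a two-df test by one averaged contrast. The two-df comparison, 54% v 81%, isolates the first.

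**The averaged contrast is a choice.** This also stands. Hypotheses 1-4 name no time point, and the mean loses badly if the effect is at one visit.

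**Balance was checked.** A non-significant homogeneity test does not remove the gain, which comes from correlation and not from imbalance.

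**ITT is stated.** It is, though without a method for missing values. A reader might infer that women with a missed visit were dropped, as classical repeated-measures ANOVA would do without imputation. The documents do not show this; the flowchart is not visible and no loss is computed here.

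**Conclusion.** The plan leaves a collected baseline score out of the group comparison as a covariate. Under compound symmetry, using it narrows the interval for the follow-up mean at all three correlations examined, by 10.5 to 27% against the change contrast and about 7 to 35% against the unadjusted mean. The size rests on assumed correlations and complete data with 37 v 35 women.

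The power figures are illustrative only, because the FS effect is back-calculated from post-hoc power, which is not independent evidence of the true effect. The power gain matters mainly for FS and SS. For Q-DASH and SUPPH, group-by-time already has 95/99/100% and 88/96/100% at the implied effects.

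This is a worthwhile improvement to the analysis. It does not show that the reported conclusions are wrong, and it does not establish that one averaged contrast must be the treatment test. The 100 per group under Randomization and the 37 and 35 under Sample size calculation do not agree. That is a separate matter to reconcile and carries no weight in this conclusion.

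**What to change.** For hypotheses 1-4:

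1. Fit a linear mixed model with months 3 and 6 as outcomes and group, visit, group-by-visit, baseline and baseline-by-visit as fixed effects, with unstructured covariance. Include all women with at least one follow-up, analysed as assigned.
2. Report the baseline-adjusted group difference with its 95% CI at each visit, and the two-df joint test of both visits. The adjusted mean of the two visits is an optional summary.
3. Do not use the three-visit group main effect as the treatment test. Label the within-arm ANOVAs and paired t-tests descriptive.
4. State which ANOVA term was read as the treatment test in the existing analysis, and the visit and purpose of the two-means test.
5. State how missing scores are handled, and add a sensitivity analysis that includes women with no follow-up, for example control-based multiple imputation or a tipping-point shift.
6. Label the re-analysis post hoc. Study design and setting gives April 2017 as the end of the study period, and Ethical aspects already reports results.

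**Cost.** No new data are needed, only another procedure in the same software (MIXED in SPSS) and revised wording. The model assumes data missing at random and leaves out women with no follow-up, hence step 5. Naming the analysis now does not restore prespecification.

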### **Study design and setting**

The study had a single-blind, randomized controlled experimental design. To avoid bias, the participants were not told whether they were in the experimental or the control group. The conceptual structure of the study is given in Figure. This randomized clinical trial was based on

the guidelines proposed by the Consolidated Standard of Reporting Trials – CONSORT 2010.

The study was conducted at homes of patients receiving treatment for breast cancer at a hospital and living in Samsun, a city in northern part of Turkey , between May 2016 and April 2017.

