### **Inclusion criteria**

The study population included individuals receiving radiotherapy after breast surgery. Inclusion criteria were diagnosis of primary breast cancer and having stage I, II and III, having axillary dissection, not having the diagnosis of lymphedema, receiving radiotherapy, volunteering to participate in the study, age over 18 years and female and residing in the city.

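### The only multiplicity-corrected follow-up test is a paired (within-arm) t-test, which cannot test hypotheses 1 to 4, and the plan does not name the group-by-time term as decisive

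*Combined protocol and SAP*

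**What the plan says.** The Statistical analysis plan lists four procedures in one sentence:

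1. The overall analysis: "Multifactorial variance analysis of repeated measures was used to compare the groups in terms of dependent variables".
2. A two-mean test: "the significance test of difference between two means to compare pretest and posttest measures". The plan does not say whether the two means are two arms or two visits.
3. A within-arm analysis: "one-way variance analysis of repeated measures to compare intragroup pretest and posttest measures".
4. The follow-up step: "t-test for dependent groups with Bonferroni correction to perform further analysis of the difference between the mean scores of the groups".

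Only the fourth carries a multiplicity correction. The section does not name the group-by-time interaction, does not say at which visit the arms are to be compared, and gives no rule for interpreting within-arm results.

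Under Hypotheses of the study, the first hypothesis reads "Extremity function restrictions will be lower in the intervention group than in the control group". Hypotheses 2 to 4 also compare intervention with control. Under Study design and setting: "The study had a single-blind, randomized controlled experimental design". The Protocol section gives both arms the same three measurements: baseline, month 3 and month 6.

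**The concern.** The follow-up test and the hypotheses do not match. A dependent-groups t-test needs pairs, and women in one randomised arm are not paired with women in the other. If the word groups in the fourth item means the arms, the test is invalid. If it means visits within an arm, the test is valid but answers a different question: whether scores moved over time.

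This matters because both arms can move for reasons unrelated to the education, such as treatment effects receding or building up, or repeated completion of the same questionnaires. Such a trend, in either direction, makes within-arm tests significant without any intervention effect. Comparing significance in one arm with non-significance in the other does not repair this, because that comparison is not a test of the difference.

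The plan leaves this route open. The closing paragraphs under Ethical aspects describe lower barriers, greater benefits and better self-efficacy after the intervention without mentioning control, although the cost statement that follows does name the control group.

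**Working it through.** **Plan's own figure.** The documents give no error rate or power for the follow-up tests. The Sample size calculation section gives 14 per group and four post-hoc powers, but no effect size, SD or test, so these cannot show which contrast was intended. They are not used here.

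**Inputs from the documents.** Arm sizes are 37 and 35 (Sample size calculation; the Randomization section gives 100 per group, and the two must be reconciled). There are three visits, hence three visit pairs per arm. The overall error level is 0.05.

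**Assumptions.** Tests are two-sided. Bonferroni is over the three pairs, so alpha = 0.05/3 = 0.0167. The true standardised change d (mean change divided by the SD of change) is the same in both arms, so there is no intervention effect. The documents give no value for d, so a range of 0.3 to 0.5 is shown.

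**Formula.** The paired t statistic has a noncentral t distribution with n − 1 degrees of freedom and noncentrality d√n. Critical values at 0.0167 are 2.511 (n = 37) and 2.518 (n = 35). At d = 0.4 the noncentralities are 0.4 × √37 = 2.433 and 0.4 × √35 = 2.366, giving probabilities of significance p1 = 0.477 (intervention) and p2 = 0.449 (control). The arms are independent, so the joint probabilities are products.

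| d | p1 | p2 | Intervention only: p1(1 − p2) | Control only: p2(1 − p1) | Arms disagree |
|---|---|---|---|---|---|
| 0.3 | 0.261 | 0.244 | 0.197 | 0.180 | 0.378 |
| 0.4 | 0.477 | 0.449 | 0.263 | 0.235 | 0.498 |
| 0.5 | 0.700 | 0.670 | 0.231 | 0.201 | 0.432 |

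**Outside that range.** At d = 0.2 the intervention arm is significant in 11% of trials, and alone in about 10%. At d = 0.8 it is significant in 99%, but alone in only about 2%, because control is nearly always significant too.

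**Within-woman correlation.** With correlation 0.5 between visits, d equals the change in units of the outcome SD. With correlation 0.7, changes of 0.3, 0.4 and 0.5 outcome SD make the intervention arm significant in 45%, 73% and 92% of trials.

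**The right contrast.** In a simulation of 20,000 trials per case under the same null (37 and 35 women, three visits), an independent-samples t-test on change from baseline to month 6 was significant at 0.05 in about 5% of trials, whatever the size of the shared change.

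**If group-by-time comes first.** In a similar simulation with correlation 0.5, requiring a significant group-by-time term first cut the intervention-only pattern to about 2% of null trials.

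**The case against.** The strongest reply is that the same sentence opens with an overall comparison of the arms, and that the two-mean test, listed apart from both the intragroup and the dependent-groups tests, may itself be an independent-samples comparison. This stands. A reader might infer that the plan settles hypotheses 1 to 4 by within-arm tests alone; the documents do not support that.

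Second, the dependent t-test directly follows the intragroup ANOVA, and Bonferroni-corrected paired tests are the usual post hoc step for such an ANOVA. The word groups may be loose wording for time points. This is plausible and would remove the invalidity. It would still leave the plan without a clearly stated, corrected between-arm follow-up.

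Third, no passage says that a within-arm change, or significance in one arm only, supports a hypothesis. This also stands. The 26 to 70% is the power of a paired test to detect a real change over time, and becomes an error rate only under that decision rule. The rule is also nearly symmetric: control alone is significant in 18 to 24% of null trials.

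Fourth, a reader might infer that these women are recovering naturally, so that bias favours the intervention. The documents do not describe an untreated course. The Inclusion criteria speak of "individuals receiving radiotherapy after breast surgery", so scores could worsen as well as improve. The argument needs only a shared trend, whose size and direction are assumptions.

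Finally, the text under Ethical aspects reports no test, so it does not show that paired tests were used.

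**Conclusion.** The point holds as a mismatch between the follow-up test and the hypotheses, together with an unnamed decisive term. Under either reading of the sentence, the paired t-test cannot support hypotheses 1 to 4. An overall between-arm analysis exists, so this is not a trial without a test of its hypotheses, and the documents do not show that any conclusion was reached by the wrong route.

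If within-arm significance were used to decide, an equal change of 0.3 to 0.5 in both arms would make the intervention arm significant in 26 to 70% of null trials, and significant while control is not in 20 to 26%. This rests on the assumed size of change, two-sided tests, three visit pairs and arm sizes of 37 and 35. It should not be quoted as the trial's false-positive rate. The change should be made, because the ambiguity bears on how four of the six hypotheses are decided.

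**What to change.** - State that hypotheses 1 to 4 are decided by the group-by-time term of the multifactorial repeated-measures ANOVA.
- Follow it with independent-groups comparisons of change from baseline at month 3 and month 6, Bonferroni-corrected for the two visits (0.05/2 = 0.025 each).
- Say whether the two-mean test compares arms or visits.
- Label the intragroup ANOVA and the paired t-tests as descriptive within-arm results that support no hypothesis.
- Word effect statements, including those under Ethical aspects, as differences from control.

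The cost is a revision of the plan's wording and a re-run on data already collected, since both arms have the same visits. The downside is that significant within-arm improvements can no longer be cited as evidence of effect. As the documents already contain results, the change should be dated and reported as made after data collection.

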### **Intervention**

Education Material; Breast Cancer Related Lymphedema Education Guide, prepared in light of the literature and revised in accordance with three experts opinions, was used at home visits. The content of the guide was directed towards supporting seriousness and sensitivity of the participants about lymphedema and created by taking account of HBM.

Home Visits; At the first home visits to the intervention group, the researcher met the participants and their families, explained the aim of the study and administered the pretests. The guide was introduced, and health education was given. Arm exercises used to prevent lymphedema were demonstrated and measurement of the arm circumference was taught. Follow-up forms were introduced and from the women were asked to do exercises as daily, make measurements as weekly, and record them in the forms day to day regularly. The arm measurements made by the researcher were included into the analysis. The participants and their families were encouraged to phone and receive counseling about things which they needed. Each home visit lasted 45 minutes on average. Three and six months after the first visit, the patients were phoned and made an appointment. At the second and the third home visits, the measurements were repeated, and the nursing interventions were maintained in the direction of the patients' individual needs (repeated of education, exercises and arm circumference measurement, control of follow-up forms).

At the first home visits in the control group, the researcher was introduced herself, explained the study and administered the pretests. The measurements were repeated in the third and sixth months after the first home visit. The women in the control group were not told about the nursing interventions, given to the intervention group, during the study period in order to

avoid bias. At the end of the sixth month, education and guide about prevention of lymphedema were offered to this group.

Reminders; In the intervention group was sent a message reminding behavior preventing lymphedema every week.

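### Intention-to-treat is credited with eliminating the effects of dropout, but it cannot supply outcomes never measured, and an intervention woman who declines further home visits has no described route to be measured

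*Combined protocol and SAP*

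**What the plan says.** On dropout, the Statistical analysis plan has one sentence: "Intention-to-treat (ITT) analysis was utilized to eliminate effects of dropouts from the study, to maintain randomization". The same section names repeated-measures analysis of variance for the group comparison. It does not say what happens when a month-3 or month-6 value is missing, and it lists no sensitivity analysis.

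On measurement, the Protocol section says of the intervention arm: "At the second and the third home visits, the measurements were repeated, and the nursing interventions were maintained", according to individual needs. The Intervention section lists the content of those visits as repeat education, exercises, arm measurement and a check of the follow-up forms. For the control arm the Protocol section says: "The measurements were repeated in the third and sixth months after the first home visit". Controls are offered the education at the end of month 6.

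Part of the intervention happens away from the visits. The women "were asked to do exercises as daily, make measurements as weekly", and the Reminders entry reads "In the intervention group was sent a message reminding behavior preventing lymphedema every week". On the arm data, the Intervention section says: "The arm measurements made by the researcher were included into the analysis". The women's own weekly readings are not named as analysis data.

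**The concern.** Intention-to-treat decides the group in which a woman is counted. It preserves the randomized comparison only so far as her outcome is known, or is handled by a stated method whose assumptions can be examined. The plan credits the principle with removing the effect of dropout and offers nothing else to deal with it.

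The visit structure makes this more than a matter of wording. In the intervention arm, follow-up measurement and continued intervention share the same visits. If a woman no longer wants those visits, no other way of obtaining her arm circumference, Q-DASH, SUPPH or QLQ-BR23 is described. Before the end of month 6 a control woman has no intervention to stop, so the link between stopping treatment and losing the outcome exists in one arm only. If the women lost differ in outcome from those kept, the comparisons for hypotheses 1 to 5 can be biased, and the plan's wording tells the reader that they are not.

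**Working it through.** **1. Does the stated property follow from the plan?** Three things could support it: continued measurement of women who stop, a missing-data method, or a sensitivity analysis. The Protocol and Intervention sections describe no measurement outside the visits, and the Statistical analysis plan gives neither of the other two. Repeated-measures analysis of variance in its conventional form needs every time point. A woman with baseline and month 3 but no month 6 would then fall out of it, whichever group she is assigned to. The property does not follow.

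**2. Who is left unmeasured?**
- Intervention woman who stops exercises, forms or reminders but accepts the visits: measured.
- Intervention woman who declines the visits: no described route.
- Control woman who refuses the visits: also not measured, but she has not stopped an intervention.

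**3. Effect on lymphedema incidence (hypothesis 5), without assuming who is lost.** Inputs: n = 37 intervention and 35 control, from Sample size calculation. The number unmeasured, u, is an assumption, because dropout counts are not available. With x cases seen among the n − u measured women:
- best case = x / n
- worst case = (x + u) / n
- width = u / n, whatever x is

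| Unmeasured, of 37 | Width |
|---|---|
| 2 | 2/37 = 5.4 points |
| 4 | 4/37 = 10.8 points |
| 7 | 7/37 = 18.9 points |
| 11 | 11/37 = 29.7 points |

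Losses in the control arm add to this. The range for the difference between arms is u1/37 + u0/35, so 4 lost in each arm gives 10.8 + 11.4 = 22.2 points.

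The Randomization section says that 100 women were assigned to each group, against 37 and 35 here. The documents do not reconcile these, so the denominator of the intention-to-treat set is itself uncertain.

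**4. Effect on the scale scores.** Let m be the share missing in an arm and k the number of SDs by which the missing women do worse than those measured. The mean of the measured women is then better than the full arm's mean by m × k, and the bias in the group difference is m1k1 − m0k0. As one example, assume no true effect, loss in the intervention arm only, and a two-sample t comparison at 0.05 two-sided with 37(1 − m) against 35. The nominal rate of a false result favouring the intervention is 2.5%.

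| m | k | Bias (SD) | False favourable result |
|---|---|---|---|
| 10% | 0.5 | 0.05 | 3.9% |
| 20% | 0.5 | 0.10 | 5.9% |
| 20% | 1 | 0.20 | 12.1% |
| 30% | 1 | 0.30 | 20.6% |

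If the loss is in the control arm instead, the sign reverses. If m × k is equal in the two arms, the bias is zero. Assigning women to their randomized group changes none of these figures.

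**The case against.** The strongest reply is that the documents do not show outcomes being lost when a woman stops the intervention. Much of the intervention is done at home, visit content followed individual needs, and nothing makes accepting education a condition of being measured. This stands. A reader might infer that any woman who stops exercising or keeping the forms becomes a dropout, but the documents do not support that. The gap concerns women who decline the visits, and even there it is inferred from the absence of another described route.

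A second reply is that loss need not be one-sided. Both arms are measured at home at months 3 and 6, and controls, who are offered nothing until the end of month 6, might leave as often or more often. This also stands. A reader might infer a bias in favour of the intervention. Suppose a fraction d is lost from that arm only, at twice the average risk, with no true effect. The risk ratio among measured women is (1 − 2d)/(1 − d): 0.89 at d = 10% and 0.75 at d = 20%. Counting the unmeasured as non-cases gives 1 − 2d: 0.80 and 0.60. The arithmetic is right, but the one-arm loss, the doubled risk and the non-case rule appear nowhere in the documents. The same loss from the control arm only would give 1/0.89 = 1.12 and 1/0.75 = 1.33.

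Third, partial data help. Every measured woman has a baseline, and some of those lost later will have a month-3 value. Methods that use these can reduce bias. The plan does not name one, and none would justify a claim of elimination.

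**Conclusion.** The point holds in a limited form. The plan claims a protection against dropout that intention-to-treat does not give, and has no missing-data rule or sensitivity analysis to stand in for it. In the intervention arm, a woman who declines further visits has no described route to outcome measurement.

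The size and direction of any bias cannot be determined from the documents. If losses were few, the practical effect is small; if they were balanced and of similar kind in both arms, the bias may be small, although the bounds remain wide. The assumption-light measure is the width for hypothesis 5: 10.8 points for 4 of 37 unmeasured and 18.9 points for 7 of 37, in the intervention arm alone. Those counts are assumed, and they rest on 37 being the right denominator. This limits what can be concluded about incidence, and about the cost comparison in so far as it depends on incidence.

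**What to change.** **Statistical analysis plan.** Replace the claim about eliminating dropout effects with a statement that all assigned women are analysed in their group using all collected data, including data collected after stopping the intervention. Say how a woman with a missing month-3 or month-6 value enters the repeated-measures analysis. Report losses and their reasons by arm. Add best-case and worst-case bounds for hypothesis 5, covering unmeasured women in both arms.

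**Protocol and Intervention sections, for the plan or any reuse of the design.** Separate stopping the intervention from withdrawing from the study. Allow a measurement-only visit in the existing month-3 and month-6 slots. Use the same 2 cm criterion for all women. Hospital diagnoses should not be substituted for those who stop, because ascertainment would then differ between women.

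**Cost.** The study setting is dated May 2016 to April 2017, so for this trial only the rewording, the reporting and the bounds can still be done. They need no new data. In a future use, measurement-only visits take slots that are already scheduled. The downside is small: the estimate may be less favourable or its range wider.
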